**Clinician Surveys:**

- The oncology provider(s) who met with the participant during the Baseline and Post-Baseline Visit will complete the survey.
- To help ensure surveys are completed in a timely manner, study staff will highlight their importance during study training and elicit clinicians' preferences for receiving and completing surveys, which will include: a HIPAA-compliant email, Redcap survey, hard copy, or in-person interview.
- The RA will administer the survey according to the provider's personal preferences within 24 hours of the visit. If not completed within 48 hours of receipt, she will leave a hard copy in the clinician's office or administer the survey during the weekly GYN research meeting.
- Estimated time to completion: 5 minutes.

**Symptom Survey:**

- Participants will be prompted by the HOPE app to complete the survey.
- The surveys will consist of single item measures of global quality of life and physical health, administered daily; the PROMIS PF 6b (6-item questionnaire about physical function) administered weekly; PRO-CTCAE questions for 10 symptoms, administered weekly (2 symptoms per day over 5 days); and a cancer experience question (audio recording), administered weekly.
- Survey items will not interfere with participants' use of their phone, but they will remain present until they are completed.
- Estimated time to completion: 3-5 minutes.
- At each subsequent visit, participants and their oncology providers will be given a summary of their survey responses since the last visit.

**Debriefing Interview:**

- The RA will conduct debriefing interviews with participants enrolled in the first phase and a subset of the patients enrolled in the second phase immediately following their completion of the final post-baseline survey (either in-person or over the phone).
- Study staff will discuss the debriefing interviews to identify opportunities for protocol improvement.
- Estimated time to completion: 5-10 minutes

**Health/Treatment Chart Abstraction:**

- The RA will review participants' medical charts to complete the Health/Tx Information form at the time of participants' baseline and post-baseline visits.
- Chart abstractions will be completed within 10 days of participants' study visits.

**Health Care Utilization Chart Abstraction:**

- The RA will review participants' medical charts to complete the Health Care Utilization form at the time of participants' baseline and post-baseline visits.
- Chart abstractions will be completed within 10 days of participants' study visits.

## 5.52 Intervention Administration

### **5.52a Smartphone App**

#### Instructional Session (*passive and active app*):

- Following the completion of the Participant Baseline Survey on Day 0, study staff will help participants download, install, and run the HOPE App on their personal smartphones.
- Participants will be prompted by Android or iOS to agree to install the app and the software will review what the app will have access to on the phone (see the participant guide). This language is part of the Android and iOS operating systems and cannot be changed. There is no way to prevent this message, which is a basic security feature in Android and reflects the broadest possible access granted to an application.
- To ensure that subjects are not misinformed, the study staff member will explain the app's privacy and data security in the *HOPE App Required Reading & Discussion* document (Appendix N). It should be noted that the discussion related to access on page 3 is specific to Android phones only.
- When the app opens, participants will register using a unique User ID and temporary password and then choose a new password. The subject will be assigned a unique 8-character Participant ID which consists of a mixture of numbers and letters. The app does not ask the subject to enter any personal information (name, date of birth, phone number, etc.) and cannot be directly linked to their DFCI health records.
- Participants will enter their oncology providers' phone numbers for the "Call my Clinician" button and enter the RA's contact number for the "Call Research Assistant" button.
- At the end of the registration process, the participant will click a button to acknowledge she has reviewed the information with the RA and provide in-app consent.
- The RA will then review how to use the app and participants will be given a copy of the *HOPE App Participant Guide-Active App* (Appendix O) or the *HOPE App Participant Guide—Passive App* (Appendix W) which describes the app and provides directions on how to use its features, frequently asked questions, as well as a review of the data that is collected and privacy measures.

#### Symptom Management (*Active app only*):

- Participants will be prompted to answer single item global measures of their quality of life and physical health daily; answer 6 questions about their physical function weekly; answer one question about their cancer experience weekly; and answer questions about 2 symptoms daily in between study visits via the HOPE App in the Symptom Survey (details in section 5.52).
- If a participant reports one or more low-risk toxicities, the app will present tailored advice on how she can manage each symptom at home. If participants report high-risk toxicities, they will be instructed that they have reported a toxicity that requires further management from their clinical team and to hit the "Call My Clinical Team" button. Please refer to the figure in section 5.53 for an overview of this process.
- After completing each survey, the app will remind participants that the results will not be reviewed by a clinician, so the survey cannot be used to communicate with study staff or to request help. The reminder will also note that if the participant feels unsafe, she should contact the treating clinician directly.

- At each clinic visit, participants and their oncology providers will be given a graphical summary of the symptoms participants reported, and/or the steps walked by participants (depending on study arm) in-between visits. The study team will provide a summary of symptoms and/or steps either by providing a hard copy during clinic or through email, depending on feasibility and provider preference. If the patient is randomized to the active app-only study arm, she and her provider will only receive symptom reporting; if the patient is randomized to the accelerometer+passive app study arm, she and her provider will only receive “step count” reporting; if the patient is randomized to the active app+accelerometer arm, she and her provider will receive both symptom and step count reporting; and if the patient is randomized to the passive app only study arm, she and her provider will not receive a symptom summary. This is dependent on patient adherence –e.g if a patient is not wearing her Fitbit or using the smartphone application and we are unable to receive step or symptom data, we will not have data to share with patients or their clinicians and no summary sheet will be provided. See Appendix V: Sample Summary Sheet for an example of what the summary data will look like. We will not monitor whether clinicians use the summary sheets, since it is difficult to reliably capture what providers read and absorb during clinic visits.

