- Hypothesis: Data collected from the wearable accelerometers and smartphone accelerometers (via passive app) will be significantly correlated with each other, and will provide quantitative measures that are correlated with patients' performance status and will be predictive of clinically significant events (hospitalizations, emergency department visits, and chemotherapy appointments)
- Hypothesis: The correlation between the wearable accelerometers and smartphone accelerometers (via passive app) will be higher in patients randomized to be encouraged to wear their smartphone at all times, and the predictive ability of the smartphone accelerometers for patients' performance status and

clinically significant events will be greater in in patients randomized to be encouraged to wear their smartphone at all times.

- Hypothesis: Participants will express more negative affect and anxiety related to their cancer experience in the weeks preceding scans, compared with the weeks when scans are not performed. This association will be moderated by participants' coping style (as measured by the brief COPE).

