#### Secondary Outcomes: Second Phase

- 1) Health care utilization (i.e. emergency room visits, hospitalizations, unplanned infusion appointments, and number of patient phone calls)
- 2) Correlation between patient and physician estimates of performance status
- 3) Additional clinical outcomes (e.g. anxiety and depression).
- 4) Correlation between data collected from the wearable and smartphone accelerometers
- 5) Predictive ability of wearable and smartphone accelerometers for patient's performance status and clinically significant events
- 6) Difference in correlation between data collected from the wearable and smartphone accelerometers, and difference in predictive ability of smartphone accelerometers for patient's performance status and clinically significant events, by whether patients are encouraged to wear their smartphones

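### In the two Fitbit arms the ECOG raters may already have seen the step counts, so the post-baseline association between steps and performance status may be inflated, and Section 6.4 does not separate those ratings

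*Combined protocol and SAP*

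**What the plan says.** All references are to Part 1, the HOPE Trial, Phase 2.

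- **Who sees steps.** Section 5.52a (Symptom Management) provides that at every clinic attendance "participants and their oncology providers will be given a graphical summary of the symptoms participants reported, and/or the steps walked by participants", varying by arm. In arm 1, "she and her provider will receive both symptom and step count reporting"; arm 2 gets steps only; arms 3 and 4 get no step report.
- **How and when.** The summary is delivered "either by providing a hard copy during clinic or through email, depending on feasibility and provider preference". If no data arrive, "we will not have data to share with patients or their clinicians and no summary sheet will be provided". The section adds: "We will not monitor whether clinicians use the summary sheets".
- **Who rates ECOG.** Both clinician and patient (5.21c). Under Clinician Surveys in 5.5.1, "The oncology provider(s) who met with the participant during the Baseline and Post-Baseline Visit will complete the survey", and the survey is administered within 24 hours of the visit. The patient's post-baseline interview is held either before or after a scheduled visit. Table 3 places both instruments at Days 30, 90 and 180.
- **What is tested.** Section 2.2 expects that the wearable and phone accelerometer data "will provide quantitative measures that are correlated with" performance status. Secondary outcome 5 in 6.1 is "Predictive ability of wearable and smartphone accelerometers" for performance status and for clinically significant events.
- **Analysis.** The Phase 2 text of 6.4 discusses prediction of clinical events and repeats analyses by the encouragement randomisation. It gives no model or metric for predicting performance status, and does not distinguish raters who have seen steps from those who have not.

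**The concern.** Section 1.2 sets out to learn whether accelerometers give valid and reliable measures of performance status, and expects walking to be an independent measure of it. That needs a reference rating formed without sight of the step data. In arms 1 and 2 the intervention itself hands the step data to both raters. If a rater uses the sheet, part of any agreement between steps and ECOG reflects reading the sheet and says nothing about the validity of steps.

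The protocol itself gives reason to expect such influence. Section 2.2 hypothesises that patient and oncologist performance-status estimates will agree more closely with the monitored wearable. For that kappa comparison, an influence of step feedback on ratings is the hypothesised effect and no flaw. For validating steps against the same ratings it is incorporation bias. At stake is a validity claim on a secondary outcome; the primary EQ-5D comparison is not involved.

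**Working it through.** The plan states no figure for this outcome, so there is nothing to reproduce. The check has three parts.

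**1. Can the raters have seen steps?**

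Arms 1 and 2 hold 25 + 25 = 50 patients (6.2). With three post-baseline visits there are up to 50 x 3 = 150 patient-visits, each with a clinician and a patient rating.

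- *Same day.* The clinician survey normally follows the visit, so a sheet handed over in clinic precedes it. An emailed sheet may not. The patient may be interviewed before the visit.
- *Earlier visits.* Sheets are given at every clinic visit, but ECOG is rated only at Days 30, 90 and 180. With visits three weeks apart (the example spacing in 1.1, taken here as an assumption), one visit falls before Day 30 (Day 21), four before Day 90 (last at Day 84) and eight before Day 180 (last at Day 168). Whatever the same-day order, raters at Days 90 and 180 will normally have seen earlier sheets.
- *Device.* Patients are taught to use the Fitbit device and app (5.52b), so they can probably see their own steps. This is an inference.

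**2. How large could the effect be?**

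Illustration only. Let S be standardised steps and R0 the uninformed rating, standardised and signed so that higher is better, with corr(R0, S) = r0. The rater gives weight w to the displayed steps: R = (1-w)R0 + wS. Then

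corr(R, S) = [(1-w)r0 + w] / sqrt[(1-w)^2 + w^2 + 2w(1-w)r0].

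For r0 = 0.40 and w = 0.2: (0.32 + 0.20) / sqrt(0.64 + 0.04 + 0.128) = 0.52 / 0.899 = 0.58.

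| r0 (assumed) | w = 0 | w = 0.1 | w = 0.2 | w = 0.3 |
|---|---|---|---|---|
| 0.30 | 0.30 | 0.40 | 0.50 | 0.61 |
| 0.40 | 0.40 | 0.49 | 0.58 | 0.67 |
| 0.50 | 0.50 | 0.58 | 0.65 | 0.73 |

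The table assumes that every rating is exposed. With r0 = 0.40, w = 0.2 and a share f exposed, the pooled correlation is [(1-f)(0.40) + f(0.52)] / sqrt[(1-f) + f(0.808)]: 0.44 at f = 25%, 0.48 at 50%, 0.53 at 75% and 0.58 at 100%.

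**3. Would the data reveal it?**

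With 50 Fitbit patients and one pair each, the 95% interval for r = 0.40 is tanh(0.424 +/- 1.96/sqrt(47)) = 0.14 to 0.61. The uninformed value is unknown, and an interval this wide contains both 0.49 and 0.58.

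A contrast of the phone-ECOG correlation in arms 1 and 2 against arms 3 and 4 (50 v 50) has a Fisher-z standard error of sqrt(1/47 + 1/47) = 0.21. For 0.58 v 0.40 the z difference is 0.239, or 1.16 standard errors: about 21% power at two-sided 5%. For 0.49 v 0.40 power is under 10%. Both are before dropout, and before dilution because phone and Fitbit data agree imperfectly.

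**The case against.** **Exposure is not established.** The interview may precede the visit, the sheet may be emailed, none is issued without data, and use is not tracked. This stands: a reader might infer that both raters always see steps before rating, but the documents do not say so. It does not remove the risk, because sheets from earlier visits remain.

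**An informed rating may be a better rating.** Section 1.2 argues that unaided estimates of performance status are unreliable and improve with shared reporting. This also stands in part: some of a higher correlation could be real gain in accuracy, and the illustration counts all of the weight on steps as contamination. But the two cannot be told apart in these ratings, so the ratings cannot by themselves show that steps are an independent measure.

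**The reach is narrow.** A reader might take the whole of secondary outcome 5 to be circular. It is not. Clinical events are not ratings. Arms 3 and 4 receive no step report. In arms 1 and 2 phone data are touched only through their correlation with Fitbit steps. Visit 0 ECOG is clear: Fitbit set-up follows the baseline survey, no between-visit summary yet exists, and 3.2 excludes patients already tracking steps.

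**Section 6.4 does not say that it pools informed and uninformed ratings.** Correct. It leaves the performance-status analysis unspecified.

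**The magnitude is assumed.** Correct. Neither r0 nor w comes from the documents, and ECOG is a coarse ordinal grade treated here as continuous.

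**Conclusion.** The concern holds in a limited form. In arms 1 and 2, patients and providers are given steps as part of the intervention and then rate the criterion against which steps are judged. No ordering rule, exposure record or separate analysis is planned. The post-baseline association between wearable steps and ECOG may therefore be inflated.

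The documents do not support the statement that it is inflated, or by how much. The rise from 0.40 to between 0.49 and 0.67 depends on assumed weights of 10% to 30% with every rating exposed; with partial exposure it is smaller, and with no weight on steps it is nil. This affects one part of one secondary outcome in a pilot. It merits a change because the change is cheap and the independence claim in 1.2 depends on it.

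**What to change.** In Section 6.4, specify the performance-status part of secondary outcome 5, including its metric, as follows.

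- **(a)** Report the phone-accelerometer v ECOG association in arms 3 and 4 as the uninformed validity estimate. It validates the phone measure and does not replace (b) for the Fitbit.
- **(b)** For the Fitbit, report Visit 0 ECOG against early steps in arms 1 and 2, with the step window fixed in advance. Call it an association: the rating precedes the steps, so it is not prediction.
- **(c)** Report post-baseline ratings in arms 1 and 2 separately, labelled as possibly informed by steps, and do not rely on them alone to claim that steps measure performance status independently.

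The phone-ECOG correlation in arms 1 and 2 may be set beside that in arms 3 and 4, descriptively only. Randomisation there identifies the total effect of the Fitbit, including changed activity, changed phone carrying and better-informed ratings. It does not isolate the circularity, and it is imprecise.

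All of this uses data already planned, so the cost is SAP wording and some extra tabulation. The downside is a smaller set, with wider intervals, for the main validity estimate. Recording at each rating whether a step summary had been seen would help further, but needs a new data item and would not undo exposure at earlier visits.

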#### App Use and Compliance (*Active and passive app*):

- Participants will be instructed to avoid adjusting the app settings to ensure data is collected. We will contact patients when we do not receive data from the app and/or Fitbit and aim to do so according to their contact preferences stated in the registration form.
- If the app is not synching properly, the RA will contact patients via text/phone/email to help resolve the issue remotely. If this is not possible, the RA will meet participants at a regularly scheduled clinic visit to download the data manually or help resolve the issue.

#### **5.52b Wearable Accelerometers:**

All participants will also receive a Fitbit Zip and Fitbit Charge 2. Participants in the Fitbit and Fitbit+HOPE App arms of Phase II of the study will receive only the Fitbit Charge 2.

#### Instructional Session:

- Following the completion of the Participant Baseline Survey on Day 0, the RA will help participants' download the Fitbit software and smartphone app, demonstrate how to use the Fitbit app and device, and teach patients how to synch the device to their smartphone. Participants will be assigned a unique study email that will be used to synch the device with the Fitbit app, as well as register the device in Fitabase (i.e., study's data collection platform).
- To reduce missing data, the RA will highlight the importance of wearing the accelerometer and review how they will be contacted by the study team, ideally through their preferred method of communication (phone/text/email), to encourage compliance. In addition to the accelerometer, participants will receive a wireless sync connector, and the *Fitbit Participant Guide* (Appendix Q), which describes proper wear and care, charging and battery life, troubleshooting instructions, uploading data, and compliance.
- The RA will encourage participants to contact study staff at any time with questions or issues to help ensure proper wear and use of the Fitbit.

**Wear Time, Compliance, and Monitoring Average Daily Steps:**

- Participants will be asked to wear the Fitbit Charge 2 on their non-dominant wrist. Study staff will continuously monitor participants wear time and data via Fitabase. We may contact patients when we do not receive data from the app and/or Fitbit and aim to contact patients according to their preferences stated in the registration form. If a Fitbit is not syncing properly, the RA will contact patients via text/phone/email to help resolve the issue remotely. If this is not possible, the RA will meet the participants in person at a regularly scheduled clinic visit to download the data manually.

**Tracking Devices:**

- The accelerometers assigned to each participant will be tracked according to the product serial number and assigned unique ID number.
- Participants will be allowed to keep the accelerometers as a token of appreciation for their participation in the study, and to minimize potential transmission of skin infections (e.g. methicillin-resistant *Staphylococcus aureus*) between participants.

**5.53 Special Concerns****5.53a Troubleshooting the HOPE App**

The intervention's participant guides outline common troubleshooting issues and how to solve them. Participants will be instructed to call study staff as soon as possible to report if they are having trouble using the app.

**5.53b Lost Accelerometers**

If a participant reports to study staff that she lost the accelerometer, study staff will provide a replacement, either in person or via mail, as soon as possible.

**5.53c Surveys**

Study staff will contact participants to complete their upcoming study survey. After three unreturned voicemails, participants will not be contacted again for additional surveys.

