#### 4.12 Informed Consent

If a patient agrees to learn more about the study, the RA will meet with the patient to describe the study, review the consent form, answer any questions, and provide her contact information. The RA will encourage patients to take their time in deciding whether they want to participate in the study or not.

If a patient is interested in participating, the RA will obtain written informed consent, which will include explaining how and why the current research study is being conducted, the study risks and benefits, the potential time commitment involved, and the option to give permission to be contacted for future research studies. The RA will explain in explicit detail what type of information will be collected from the smartphone application and wearable accelerometers and how these data are monitored. The RA will reiterate that the data collected are not a part of the patient's standard treatment and will underscore the importance placed upon maintaining patient confidentiality and a patient's rights while involved in the study, including the right to withdraw participation at any time for any reason during the study because participation is completely voluntary.

The informed consent form will contain a section dedicated to explaining what constitutes PHI and how this information will be protected as confidential per HIPAA guidelines. The consent form will also provide contact information for both the Principal Investigator (PI) as well as the Office for the Protection of Research Subjects. All informed consent processes will adhere to the policies set forth by the Institutional Review Board. Signed informed consent forms will be stored in a locked file cabinet to maintain the privacy of all study participants.

If a patient is unsure if she would like to participate in the study, she will be offered the consent form to review and a postage paid *opt-out card* (Appendix A) to notify study staff that she is not interested. If no contact is made after a few days, the RA will call the patient. If the patient decides to participate, the RA will meet her at a subsequent appointment to obtain informed consent. If a patient is not interested, the RA will thank her for considering, reassure the patient that the process will have no impact on her care. No further interactions will occur with patients who either decline or prove ineligible for the study. Patients will not be contacted after three unreturned voicemails.

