#### **4.2 Subject Registration and Randomization**

During both phase I and phase II of the study, the RA will register eligible participants in the Clinical Trials Management System (CTMS) OnCore. Registrations will occur prior to beginning study interventions. Any participant not registered to the protocol before study interventions have begun will be considered ineligible and registration will be denied. An investigator will confirm eligibility criteria and a member of the study team will complete the protocol-specific eligibility checklist.

Following registration, participants may begin study interventions. Issues that would cause delays in interventions should be discussed with the Overall Principal Investigator (PI). If a participant does not receive study interventions following registration, the participant's registration on the study will be canceled. Registration cancellations will be made in OnCore as soon as possible. After obtaining informed consent, participants will be assigned a unique study ID and registered to the study in Redcap.

The following information will be recorded for each participant in the *Registration Form* (Appendix B):

- Name and telephone number of RA enrolling the participant
- Date participant signed consent and RA who obtained consent
- Participant's study ID and first and last initials
- Participant's date of birth
- Participant's primary oncology providers
- Confirmation that participant meets eligibility criteria
- Name of oncology provider who approved participant's eligibility and date of approval
- Participant's contact preferences (phone call, text, or e-mail; collected post-consent)
- Participant's study arm (to be completed after randomization)

In the second phase, the study team will randomize enrolled participants to one of the four arms: 1) Fitbit+active app, 2) Fitbit+passive app, 3) Active app, or 4) Passive app —using a 1:1:1:1 ratio using a computer-generated random allocation sequence with blocks of 8 in order to maintain balance between study arms over time. Study staff will generate group assignments in sequentially numbered and sealed opaque envelopes. Please refer to the protocol schema for details.

[figure not shown]

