#### Participant Post-Baseline Interview:

- The RA will administer the interview to participants via an in-person interview before or after a regularly scheduled visit that falls as close to the projected assessment date as possible (Post-Baseline Visit).
- Every effort will be made to administer the interview in-person and on the date of the Post-Baseline Visit. If this is not feasible, participants will complete it over the phone as close to the visit date as possible.
- To encourage participation and reduce the number of incomplete interviews, participants will be contacted prior to their visit to confirm the date of their upcoming visit and interview.
- Estimated time to completion: 30 minutes.

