## 6.5 Handling of Missing Data

For the primary quality-of-life analysis, we will exclude from our analyses any patients who do not complete any post-baseline EQ-5D questionnaires and carry forward the last post-baseline observation available for patients without 6-month data. If >10% of participants have missing data from the 6-month survey, we will perform sensitivity imputation analyses including: 1) no observations carried forward, 2) minimum observation values carried forward, 3) average observation values carried forward, and 4) last observation carried forward, but with an EQ-5D value of 0 if death occurred before 6 months.

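### Section 5.53c ends survey contact after three unreturned voicemails with no restart, which blocks the pre-visit contact and phone fallback of 5.5.1 and can cost a 6-month EQ-5D

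*Combined protocol and SAP*

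**What the plan says.** All references are to Part 1, the HOPE Trial.

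- **5.53c Surveys** has staff contact participants about the survey that is coming up, and then sets a limit: "After three unreturned voicemails, participants will not be contacted again for additional surveys".
- **5.5.1, Participant Post-Baseline Interview**, sets the normal route: "Every effort will be made to administer the interview in-person and on the date of the Post-Baseline Visit". It adds a fallback: "If this is not feasible, participants will complete it over the phone as close to the visit date as possible". To limit incomplete interviews, it also says that "participants will be contacted prior to their visit to confirm the date of their upcoming visit and interview".
- **4.12 Informed Consent** has a similar limit for patients who are still deciding whether to join: "Patients will not be contacted after three unreturned voicemails".
- **4.2** has the registration form record whether each participant prefers phone, text or e-mail.
- **5.4, Table 3** places the post-baseline interview at days 30, 90 and 180 in all four arms. Table 1 includes the EQ-5D-5L in that interview.
- **6.1** makes the comparison of baseline and 6-month EQ-5D the primary endpoint of the second phase.
- **6.5** deals with gaps in two ways: "we will exclude from our analyses any patients who do not complete any post-baseline EQ-5D questionnaires", and for the rest the plan is to "carry forward the last post-baseline observation available for patients without 6-month data". Sensitivity analyses follow only if more than 10% of participants lack the 6-month survey.

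**The concern.** Section 5.53c starts from one upcoming survey but ends contact for later surveys in general. Nothing restarts the count at the next assessment, nothing exempts day 180, and nothing treats three unreturned voicemails as withdrawal. A limit of this kind suits a patient who is still considering enrolment, as in 4.12. It has not been adapted to an enrolled patient with three scheduled assessments, the last of which carries the primary endpoint.

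Section 5.5.1 relies on two forms of remote contact to keep interviews from being missed: contact before the visit, and a telephone interview when the in-person one is not feasible. Once 5.53c has been triggered, both are closed for every later assessment, and no passage says which section prevails. What is at stake is an observed 6-month EQ-5D in a patient who never withdrew and might have answered months later.

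**Working it through.** The documents give no figure for how often three voicemails go unreturned. The check therefore sets the passages side by side and follows one patient through them.

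**1. The narrower reading of 5.53c.** Suppose the limit covers only remote outreach, so that staff may still approach the patient at a clinic visit. Compare this with 5.5.1 at a later assessment:

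| Route in 5.5.1 | After 5.53c is triggered, narrower reading |
|---|---|
| In-person interview at a regular visit | Open |
| Contact before the visit | Blocked |
| Telephone interview if in-person is not feasible | Blocked |

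The conflict over the last two routes remains even on the reading most favourable to the plan.

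**2. What reaches the primary analysis.** The inputs are the visit days in Table 3 and the rule in 6.5. The age of a carried value is 180 minus the day it was obtained. The table assumes no in-clinic interview after the round in which the rule is triggered.

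| Round in which the rule is triggered | Post-baseline EQ-5D held | Later assessments without contact | 6-month value under 6.5 |
|---|---|---|---|
| Day 30 | Day 30 | Days 90 and 180 | Day 30 value, 180 − 30 = 150 days old |
| Day 30 | None | Days 90 and 180 | Patient excluded |
| Day 90 | Day 90 | Day 180 | Day 90 value, 180 − 90 = 90 days old |
| Day 90 | Day 30 only | Day 180 | Day 30 value, 150 days old |
| Day 90 | None | Day 180 | Patient excluded |

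Triggered at day 30, the rule ends contact for two of the three post-baseline assessments. Triggered at day 90, it ends contact for the last one. Triggered at day 180, it affects no later HOPE assessment.

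**3. Whether 6.5 would reveal it.** With 100 patients, more than 10% means at least 11 missing 6-month surveys. Up to 10 such losses would start no sensitivity analysis. That threshold is a general choice in 6.5 and not a result of 5.53c, but it means a modest number of losses would pass without further examination.

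**4. Contact channel.** The trigger counts voicemails only. Read literally, a patient who is reached by text or e-mail never triggers it. Equally, a patient who asked for texts could be telephoned three times and then dropped, because 5.53c does not require her recorded preference to be tried first.

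**The case against.** The strongest reply is that a specific limit ordinarily qualifies a general promise. Section 5.53c sits under Special Concerns, and making every effort cannot mean contacting without end. Three unanswered voicemails from a patient with incurable cancer may be a reasonable sign that she does not want to be called. Clinic contact also continues: under 5.52, staff give symptom or step summaries at clinic visits in arms 1 to 3 where data exist, and resolve app or Fitbit problems there. In the rows of the table where a value is obtained in the triggering round, the likeliest explanation is an interview in clinic, and the same route is open at day 180.

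Much of this stands. Limiting calls is a defensible choice. A reader might infer that 5.53c forbids the in-person interview, or that triggering it by itself loses the endpoint. The documents do not support this: a rule that counts voicemails can reasonably be read as governing remote contact only, and the loss also requires that the patient is not interviewed in clinic. But the text does not state the narrower reading. Even if it did, the routes designed for a patient who cannot be interviewed at a visit would still be closed.

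It may also be said that section 5.5 introduces its procedures as those of the first phase. It nevertheless sets second-phase procedures too, such as the second-phase debriefing interviews and the arm-specific summaries. The first phase has a single post-baseline interview (Table 2), so a rule about later surveys matters mainly in the second.

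**Conclusion.** The point holds as a gap in 5.53c that should be reconciled with 5.5.1. A contact rule, and not a decision by the patient, can leave the primary endpoint to a value 90 or 150 days old or remove the patient from the analysis. This rests on three conditions: 5.53c is followed as written, the patient has not withdrawn, and she is not interviewed in clinic. How often they coincide is unknown, and the interviews at regular visits make it less likely. No overall effect on the trial result is claimed.

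A reader might also infer that the power in 5.12 and 6.2 is overstated because of such losses. The documents do not support that. For 50 against 50, SD 14 and one-sided 5%, the standard error is 14 × √(2/50) = 2.8. Power is Φ(6/2.8 − 1.645) = 69.1% for 6 points and Φ(7/2.8 − 1.645) = 80.4% for 7, against the stated 70% and 80%. The basis of 100 patients is stated, the documents give no loss rate, and a patient whose earlier value is carried forward still counts towards the 100. The power statements need no change on this account.

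**What to change.** In 5.53c:

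1. Apply the three-voicemail limit to each assessment separately.
2. Approach the patient again at day 90 and day 180, in person at scheduled visits and by the contact preference recorded at registration, unless she has withdrawn or asked not to be contacted.
3. State that 5.5.1 governs otherwise.

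This takes one or two sentences. A patient who triggers the limit at day 30 would face at most two further rounds, 2 × 3 = 6 voicemails. One who triggers it at day 90 would face at most one, 1 × 3 = 3. Existing staff can do this. The downside is a small added burden on ill patients, which a request for no contact ends. Section 5.5 lets study activities be adapted without an amendment where the principal investigator determines that there is no additional risk, so the change may not need one. No change to the sample size or to 5.12 and 6.2 is proposed.
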